### **3.3. Study Definitions and Derived Variables**

Individual subject titers are calculated by taking the geometric mean of two replicate results at each time point.

For individual subjects, fold rise will be calculated as the ratio of:  $\frac{\text{post-vaccination titer}}{\text{pre-vaccination titer}}$  where pre-vaccination value is always the result obtained at Day 1, prior to the priming vaccination.

Seroconversion for HAI and Neut assays is defined as either a pre-vaccination titer <10 and a post-vaccination titer  $\geq 40$ , or a pre-vaccination titer  $\geq 10$  and a minimum four-fold rise in post-vaccination titer [5].

---

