### 4.4.3. Method of Assigning Subjects to Treatment Groups (Randomization)

Enrollment/randomization will be performed through the enrollment module in the electronic data capture system maintained by the Statistical and Data Coordinating Center (SDCC).

Eligible subjects will be stratified by prior receipt of 2013 A/H7N9 IIV with or without adjuvants, clinical site, and prior receipt of licensed, seasonal influenza vaccine then randomly assigned with allocation (1:1) to one of two treatment arms to receive 1 dose of 2017 A/H7N9 IIV at 3.75 mcg HA per dose with or without AS03 adjuvant. There is a total of ten strata with maximum enrollments outlined in [Table 1](#).

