### 6.3.2. Modified Intent-to-Treat (mITT) Population

The modified intent-to-treat (mITT) population includes all subjects who received study vaccination and contributed both pre- and at least one post-vaccination venous blood samples for immunogenicity testing (HAI and Neut antibody assays) for which valid results were reported. For analyses using the mITT population, any subject receiving a product that is different than the one they were randomized to receive will be examined and grouped on a case by case basis.

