## **6.7. Multicenter Studies**

Although randomization was stratified by site, data will be pooled across all clinical sites for all analyses. Center effects are not anticipated because the sites are using standardized procedures for vaccination and assessment of solicited and unsolicited AEs, and the study relies on a central laboratory for immunogenicity assessments.

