### 8.3.2. Regression Modeling

Logistic and multivariable linear regression will be utilized to test for the effects of prior vaccination with 2013 A/H7N9 IIV and the addition of AS03 adjuvant to 2017 A/H7N9 IIV on seroconversion and GMT at 21 days post vaccination, respectively, for the PP population. Similar models will be fit for both HAI and Neut antibody results.

Logistic regression will be fit to examine the relationship of HAI seroconversion at 21 days post vaccination with study group, stratum, and the interaction of study group and stratum. If the available titer data meets the required assumptions of normality after log transformation, multiple linear regression will be fit to examine the relationship of log transformed titers at 21 days post vaccination with study group, stratum, and the interaction of study group and stratum. Both models will be fit with and without adjustment for the following covariates (*Z*): sex (female, male), age (19-35 years, 35-50 years, 51-70 years), BMI (<30, ≥30), and prior receipt of seasonal influenza vaccine (none in past 2 seasons, at least one in past 2 seasons). Modeling assumptions will be checked using standard diagnostic methods (e.g., using the INFLUENCE option in PROC LOGISTIC or PROC GLM). Parameter estimates and odds ratio estimates for the logistic models will be presented in [Table 36](#), [Table 37](#), [Table 38](#), and [Table 39](#). Parameter estimates for the multiple linear regression models will be presented in [Table 40](#), [Table 41](#), [Table 42](#), and [Table 43](#).

Model 1A: Logistic Regression (without covariate adjustment):

$$\text{logit}[P(\text{seroconversion})] = \beta_0 + \beta_1 \times \text{Study Group} + \beta_2 \times \text{Stratum} + \beta_3 \times \text{Study Group} * \text{Stratum}$$

Model 1B: Logistic Regression (with covariate adjustment):

$$\text{logit}[P(\text{seroconversion})] = \beta_0 + \beta_1 \times \text{Study Group} + \beta_2 \times \text{Stratum} + \beta_3 \times \text{Study Group} * \text{Stratum} + \beta_4 \times Z$$

Model 2A: Multiple Linear Regression (without covariate adjustment):

$$\log(\text{titer}) = \beta_0 + \beta_1 \times \text{Study Group} + \beta_2 \times \text{Stratum} + \beta_3 \times \text{Study Group} * \text{Stratum} + \varepsilon$$

Model 2B: Multiple Linear Regression (with covariate adjustment):

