Time Point	2013 A/H7N9 IIV + MF59 (N=X)		2013 A/H7N9 IIV + AS03 (N=X)		2013 A/H7N9 IIV 15 mcg or 45 mcg unadjuvanted (N=X)		2013 A/H7N9 IIV with MF59/AS03 then 2013 A/H7N9 IIV 15 mcg (N=X)		A/H7 IIV Naïve (N=X)	
	3.75 mcg A/H7N9 (N*=X)	3.75 mcg A/H7N9 + AS03 (N*=X)	3.75 mcg A/H7N9 (N*=X)	3.75 mcg A/H7N9 + AS03 (N*=X)	3.75 mcg A/H7N9 (N*=X)	3.75 mcg A/H7N9 + AS03 (N*=X)	3.75 mcg A/H7N9 (N*=X)	3.75 mcg A/H7N9 + AS03 (N*=X)	3.75 mcg A/H7N9 (N*=X)	3.75 mcg A/H7N9 + AS03 (N*=X)
GMFR (95% CI) a	xxx.x (xxx.x,xxx.x)	xxx.x (xxx.x,xxx.x)	xxx.x (xxx.x,xxx.x)	xxx.x (xxx.x,xxx.x)	xxx.x (xxx.x,xxx.x)	xxx.x (xxx.x,xxx.x)	xxx.x (xxx.x,xxx.x)	xxx.x (xxx.x,xxx.x)	xxx.x (xxx.x,xxx.x)	xxx.x (xxx.x,xxx.x)
Seroconversion - % (95% CI) b	xx (xx, xx)	xx (xx, xx)	xx (xx, xx)	xx (xx, xx)	xx (xx, xx)	xx (xx, xx)	xx (xx, xx)	xx (xx, xx)	xx (xx, xx)	xx (xx, xx)
180 Days Post Vaccination										
n	x	x	x	x	x	x	x	x	x	x
GMT (95% CI) a	xxx.x (xxx.x,xxx.x)	xxx.x (xxx.x,xxx.x)	xxx.x (xxx.x,xxx.x)	xxx.x (xxx.x,xxx.x)	xxx.x (xxx.x,xxx.x)	xxx.x (xxx.x,xxx.x)	xxx.x (xxx.x,xxx.x)	xxx.x (xxx.x,xxx.x)	xxx.x (xxx.x,xxx.x)	xxx.x (xxx.x,xxx.x)
Titer ≥ 1:40 - % (95% CI) b	xx (xx, xx)	xx (xx, xx)	xx (xx, xx)	xx (xx, xx)	xx (xx, xx)	xx (xx, xx)	xx (xx, xx)	xx (xx, xx)	xx (xx, xx)	xx (xx, xx)
GMFR (95% CI) a	xxx.x (xxx.x,xxx.x)	xxx.x (xxx.x,xxx.x)	xxx.x (xxx.x,xxx.x)	xxx.x (xxx.x,xxx.x)	xxx.x (xxx.x,xxx.x)	xxx.x (xxx.x,xxx.x)	xxx.x (xxx.x,xxx.x)	xxx.x (xxx.x,xxx.x)	xxx.x (xxx.x,xxx.x)	xxx.x (xxx.x,xxx.x)
Seroconversion - % (95% CI) b	xx (xx, xx)	xx (xx, xx)	xx (xx, xx)	xx (xx, xx)	xx (xx, xx)	xx (xx, xx)	xx (xx, xx)	xx (xx, xx)	xx (xx, xx)	xx (xx, xx)

Note: N = Number of subjects in the modified intent-to-treat population in the given stratum; N\* = Number of subjects in the modified intent-to-treat population in the given stratum and study group; n = number of subjects with available results; GMT = Geometric Mean Titer; GMFR = Geometric Mean Fold Rise.

a Confidence Interval calculated based on the student's T distribution.

b Exact binomial confidence interval calculated using the Clopper-Pearson methodology.

Tables with similar format:

**Table 23: Summaries of Hemagglutination Inhibition Antibody Against A/Hong Kong/125/2017 (H7N9) by Study Day, Stratum and Study Group, Per Protocol Population\***

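### The linear titre models in SAP 8.3.2 leave out the Day 1 titre and define no per-stratum or averaged AS03 contrast: a minor loss of precision and clarity, not a bias

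*SAP*

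**What the plan says.** SAP 8.3.2 states that the regressions will be "utilized to test for the effects of prior vaccination with 2013 A/H7N9 IIV and the addition of AS03 adjuvant", in the per-protocol (PP) population, for both HAI and Neut. Model 2A has study group, stratum and their interaction. On covariates the section says "Both models will be fit with and without adjustment for the following covariates", and Model 2B adds "sex (female, male), age (19-35 years, 35-50 years, 51-70 years), BMI (<30, ≥30), and prior receipt of seasonal influenza vaccine". The linear models are fitted only if log titres meet the normality assumption.

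The Day 1 titre is available and used elsewhere:
- The mITT population, from which the PP population is drawn, requires subjects who "contributed both pre- and at least one post-vaccination venous blood samples for immunogenicity testing" (SAP 6.3.2).
- Fold rise is defined in SAP 3.3 as a ratio "where pre-vaccination value is always the result obtained at Day 1", and the Table 22 shell tabulates it ("GMFR = Geometric Mean Fold Rise").

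Randomisation is "stratified by prior receipt of 2013 A/H7N9 IIV with or without adjuvants, clinical site, and prior receipt of licensed, seasonal influenza vaccine" (SAP 4.4.3), then 1:1. On site, SAP 6.7 says: "Although randomization was stratified by site, data will be pooled across all clinical sites for all analyses". It gives standardised procedures and a central laboratory as the reason.

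The shells for the titre models (SAP Tables 40-43) set the naïve stratum and unadjuvanted vaccine as references. Study group has two levels there, but ten in SAP 4.4.5 and 6.1. SAP 8.1 refers modelling of the primary endpoints to 8.3.2 and plans no formal hypothesis test; 8.3.2 itself sits under the exploratory analyses.

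Protocol 2.2 names comparison of priming regimens, AS03 against MF59 included, as something the trial will assess. Protocol Table 10 shows where the primed subjects come from; SAP Table 4 omits that column.

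**The concern.** Three things are left open.

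1. A baseline titre is usually a useful covariate for a post-vaccination titre. Here it is collected on everyone in the model and then not used in it, so the AS03 intervals may be wider than the data require.
2. With an interaction in the model, the AS03 row describes the reference stratum alone. That stratum is among the smallest, and it is the one without priming. A reader could take its row for the trial's AS03 effect.
3. AS03 and priming are tested in one sentence and printed in one format, yet only AS03 is randomised. Nothing beside the stratum rows tells the reader this, or that the MF59- and AS03-primed strata draw on different earlier trials.

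**Working it through.** **The plan's own figure.** The documents give no precision figure for Models 2A/2B. The nearest is Protocol Table 13 (SAP Table 7): 50 per arm, 0.20 v 0.46, 80% power. Exact enumeration of the two-sided likelihood-ratio test at 0.05 gives 80.1%, so it reproduces.

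**Inputs.** Arm sizes from Protocol Table 1: three strata of 50 v 50, two of 30 v 30 (mixed priming and naïve). Titres below 10 are set to 5 (SAP 4.5.2). Assumed, because not given: r (within-cell correlation of Day 1 and Day 22 log titre), the share of baselines at the floor, site ICC, and one residual SD across all ten cells.

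**AS03 effect under Model 2A, in residual-SD units**
- Naïve stratum, the printed row: sqrt(2/30) = 0.258.
- A 50 v 50 stratum: sqrt(2/50) = 0.200.
- Equal-weight average of five strata: sqrt(3 × 0.04 + 2 × 0.0667)/5 = sqrt(0.2533)/5 = 0.101.

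The printed row's SE is 0.258/0.101 = 2.6 times that of the average. At 80% power and two-sided 0.05 (2.80 × SE), the detectable effects are 0.72 and 0.28 SD.

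**Adding Day 1 titre**
- Primed stratum, no flooring: SE falls by 1 − sqrt(1 − r²), which is 4.6% at r = 0.3 and 13.4% at r = 0.5.
- Naïve stratum, all baselines at the floor: no gain.
- Averaged effect: the primed strata contribute 3 × 0.04 + 0.0667 = 0.1867 of the 0.2533. The SE ratio is sqrt((0.1867(1 − r²) + 0.0667)/0.2533), a fall of 3.4% at r = 0.3 and 9.7% at r = 0.5.
- With 80-95% of primed baselines at the floor (log2 baseline SD of 1.5 assumed), a latent r of 0.5 becomes an observed r of 0.356 to 0.232. The averaged SE then falls by 4.8% to 2.0%. For latent r = 0.3 the fall is 1.7% to 0.7%.
- A simulation of the 420-subject interaction model (3,000 trials per case, no flooring in the primed strata) gave 3.0% and 10.1% for the averaged effect at r = 0.3 and 0.5, and 0% in the naïve stratum.

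**Bias.** In a separate simulation with floored two-fold titres, the AS03 estimate was the same without and with Day 1 titre: 1.390 v 1.389, and 1.464 v 1.461 log2 units.

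**Adding site.** Simulated change in the averaged SE: +0.3% at ICC 0, −0.6% at 0.02, −1.9% at 0.05, −4.2% at 0.10.

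**Source of primed subjects (Protocol Table 10)**
- MF59 stratum: 13-0032 arms 1-3 and 13-0033 arm 8; 396/4 = 99 first doses per arm.
- AS03 stratum: 13-0033 arms 1-3 only; 291/3 = 97 per arm.
- With equal return assumed, about 75% of the MF59-primed but none of the AS03-primed subjects come from 13-0032.
- Cost of a source-protocol term, mixed stratum left out: within-cell sum of squares 100 × 0.75 × 0.25 + 100 × 0.5 × 0.5 = 43.75; added variance 0.75²/43.75 = 0.01286. The MF59-v-AS03 SE goes from 0.200 to sqrt(0.04 + 0.01286) = 0.230 (+15%) within one boost arm, and from 0.141 to sqrt(0.02 + 0.01286) = 0.181 (+28%) averaged over boost arms.

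**The case against.** The strongest reply is that nothing here is wrong. The AS03 estimate is unbiased, the models are exploratory in both documents, and leaving out site is a reasoned choice. Arm-level fold rise already uses the baseline, and SAP Tables 26-27 show both arms side by side in each stratum with confidence intervals. The gain from Day 1 titre is probably at the small end: Protocol 2.2 says the 2013 vaccine does not induce protective antibody to the newer lineage, so many baselines may be at the floor. The shells do fix which AS03 effect is printed, and each stratum's point estimate follows by adding the interaction row. No row compares MF59 with AS03 priming, and no objective or outcome measure names that comparison.

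Most of this stands, and it is why the point is minor. Two things remain. A randomised contrast can be tightened at almost no cost with data in hand. And the model tables print no interval for the AS03 effect in any primed stratum, nor for the average.

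Three stronger readings should be set aside:
- That omitting Day 1 titre or site biases the AS03 effect. Allocation is 1:1 within strata, so it does not, apart from whatever small effect PP exclusions (assumed up to 3%) may have.
- That MF59-v-AS03 priming is completely confounded with source protocol. One MF59 arm comes from 13-0033, so it is heavily but not completely confounded.
- That a source-protocol effect exists. The documents do not show one.

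**Conclusion.** The point holds as a minor one. Models 2A/2B forgo some precision on a randomised, unbiased AS03 effect: about 1-5% of the averaged SE if 80-95% of primed baselines are at the floor, about 10% at r = 0.5 without flooring, and about nothing in the naïve stratum. These figures rest on assumed correlations and floor shares and on a common residual SD. The clearer gap is in presentation: the one AS03 row is the 30 v 30 naïve effect (SE 0.258 SD), and the averaged contrast the design supports (SE 0.101 SD) is not defined.

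The priming rows need a statement that they are not randomised comparisons and that source protocol differs between strata. A reader might infer that a source-protocol adjustment is required. The documents do not support that: within a stratum the term compares different source arms, so it cannot separate protocol from regimen. No claim is made about the logistic models.

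**What to change.** 1. Add one linear model, used only for AS03 contrasts: Model 2B plus Day 1 log titre (same assay and strain), for HAI and for Neut, under the same normality condition as 2A/2B. Site may be added but is optional.
2. Print the AS03 contrast with its confidence interval in each stratum and averaged over strata, and state the weights.
3. Note beside the stratum rows that priming history is not randomised, that AS03-primed subjects all come from 13-0033, and that MF59-primed subjects come from three 13-0032 arms and one 13-0033 arm. Take priming contrasts from the model without Day 1 titre, because the baseline is partly a result of priming.
4. Optional and exploratory: an MF59-v-AS03 priming analysis with a source-protocol term, leaving out the mixed stratum, with its SE beside the main estimate and the limits above stated.

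Cost: SAP wording, a few extra fits and tables, and one degree of freedom for titre (nine more if all ten site columns of SAP Table 17 are used). No new visits or assays are needed. Item 4 would also need a source-protocol field, which Listing 6 lacks but which could be derived from the record for inclusion criterion 14, and it would raise the SE of that contrast by about 15-28%.

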Vital signs (oral temperature, pulse and blood pressure [BP]) will be collected at the screening visit (optional) and prior to study vaccination. Vital signs may be obtained if indicated at approximately 1, 3 and 7 days after study vaccination (this may only occur approximately 7 days after study vaccination for sites not processing blood for PBMCs isolation). Vital signs assessed on Day 1 prior to study vaccination will be considered as baseline. Subjects must not eat or drink anything hot or cold, or smoke within 10 minutes prior to taking oral temperature.

Height and weight will be collected at the screening visit (optional) or on Day 1 prior to study vaccination for the calculation of BMI.

Reactogenicity assessments will include an assessment of solicited AEs occurring from the time of study vaccination through 7 days after study vaccination, which includes an assessment of

injection site reactions including pruritus, ecchymosis, erythema, induration, edema, pain, and tenderness as well as systemic reactions including fever, feverishness, fatigue, malaise, myalgia, arthralgia, headache, and nausea. Pre-administration reactogenicity assessments will be performed immediately prior to study vaccination to establish baseline, then the study vaccination will be given.

Subjects will be observed in the clinic for at least 20 minutes after study vaccination. The study vaccination site will be examined, post-administration reactogenicity assessments will be performed, and any AE/SAEs will be recorded on the appropriate DCF prior to discharge from the clinic. The study vaccination site will also be examined approximately 1, 3 and 7 days after study vaccination (this will only occur approximately 7 days after study vaccination for sites not processing blood for PBMCs isolation).

All subjects will complete a Memory Aid from the time of study vaccination through 7 days after study vaccination. Memory Aids will be reviewed with the subjects for any AEs (solicited injection site and systemic reactions as well as unsolicited AEs), SAEs and concomitant medications (including solicitation for receipt of any non-study influenza vaccines) approximately 1, 3 and 7 days after study vaccination via phone call or clinic visit.

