##### **3.1.3. Exploratory**

###### Immunogenicity:

- To assess the effects of age, sex, body mass index (BMI), and prior receipt of seasonal or non-study pandemic influenza vaccine(s) on serum HAI and Neut antibody responses following receipt of the study vaccine.
- To determine, in at least a subset of samples, the serum antibody responses to N9 neuraminidase (NA).
- To assess, in at least a subset of samples, hemagglutinin (HA) stem-specific antibody responses.
- To assess, in at least a subset of samples, the cross-reactivity of serum HAI and Neut antibody responses to antigenically drifted variants of influenza A/H7 viruses.

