## 6.4. Covariates and Subgroups

As a protocol defined exploratory analysis, HAI and Neut antibody response following vaccination will be summarized stratified by the following covariates: age (categorical: 19-35, 36-50, 51-70), sex (male, female), body mass index (<30, ≥30), and prior receipt of seasonal influenza vaccine(s) (receipt of 2017-2018 or 2018-2019, or receipt of neither), and these covariates will be considered in statistical modeling as described in Section 8.3. As these analyses are exploratory the study was not powered for any subgroup analyses.

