### 9.1. Demographic and Other Baseline Characteristics

Summaries of age, sex, ethnicity, race, BMI, and prior receipt of seasonal influenza vaccine will be presented by site in [Table 17](#) and [Table 18](#) and by study group and stratum in [Table 19](#) and [Table 20](#). Age will be summarized as a continuous variable as well as by categories as defined in Section 8.3.1. Ethnicity is categorized as Hispanic or Latino, or not Hispanic or Latino. In accordance with NIH reporting policy, subjects may self-designate as belonging to more than one race or may refuse to identify a race, the latter reflected in the electronic case report form (eCRF) as “No” to each racial option. BMI will be summarized as continuous as well as categorical, categorized as (<30, ≥30). Self-reported history of prior receipt of seasonal influenza vaccine will be categorized as follows: both 2017-2018 and 2018-2019, 2017-2018 only, 2018-2019 only, receipt of none, or unknown. Demographic information for individual subjects will be provided in [Listing 6](#).

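### Models 1B and 2B enter BMI only as <30/≥30 and age only in three bands, although both are available as continuous values and no other planned model estimates their effects

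*SAP*

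**What the plan says.** The exploratory objective in SAP Section 3.1.3, repeated from Protocol Section 3.1.3, is "To assess the effects of age, sex, body mass index (BMI), and prior receipt of seasonal or non-study pandemic influenza vaccine(s") on HAI and Neut responses.

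SAP Section 8.3.2 fits a logistic model for seroconversion and a linear model for log titer at 21 days: "Both models will be fit with and without adjustment for the following covariates". The covariates begin "sex (female, male), age (19-35 years, 35-50 years, 51-70 years), BMI" (<30, ≥30). The shells of Tables 38 and 42 show the same levels, and Tables 39 and 43 follow their format.

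Both variables exist in finer form. Protocol Section 7.1: "Height and weight will be collected at the screening visit (optional) or on Day 1 prior to study vaccination for the calculation of BMI". SAP Section 9.1: "BMI will be summarized as continuous as well as categorical, categorized as (<30, ≥30"). That section treats age in the same way. The continuous versions appear only in the baseline tables.

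SAP Section 6.4 sets the bands as "age (categorical: 19-35, 36-50, 51-70), sex (male, female), body mass index (<30, ≥30"). Its middle age band starts at 36. Sections 8.3.1 and 8.3.2 and the table shells start it at 35, the last year of the first band.

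**The concern.** The coding treats a subject with a BMI of 29.9 like one with 20, and a 51-year-old like a 70-year-old. If response changes gradually with age or BMI, that gradient is estimated less precisely than the data allow. This bears on a listed objective: Tables 28-29 and 32-33 describe response by age and BMI category, but only Models 1B and 2B attach an effect estimate, confidence interval and p-value to either variable. The SAP gives no reason for the cut points.

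There is also a coding fault. Under Section 8.3.2 a 35-year-old belongs to two age bands.

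**Working it through.** The plan gives no power, precision or information figure for age or BMI, so there is nothing of its own to reproduce. The results below rest on stated assumptions.

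**Inputs.** From the documents: up to 420 subjects, up to 3% excluded from the per-protocol analysis (SAP Section 5), ages 19 to 70, two-sided alpha 0.05 (as in SAP Section 5). Assumed: a linear effect on the model scale, roughly normal BMI, and a share p of subjects at or above 30.

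**BMI.** The fraction of information kept on a linear effect is the squared correlation between BMI and its indicator, R = φ(z)² / [p(1 − p)], where z is the standard normal quantile at 1 − p.

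| Share p with BMI ≥30 | φ(z) | R (kept) | Lost |
|---|---|---|---|
| 20% | 0.2800 | 0.490 | 51% |
| 25% | 0.3178 | 0.539 | 46% |
| 35% | 0.3704 | 0.603 | 40% |
| 40% | 0.3863 | 0.622 | 38% |
| 50% | 0.3989 | 0.637 | 36% |

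For example, at 25%: 0.3178² / (0.25 × 0.75) = 0.1010 / 0.1875 = 0.539. With a lognormal BMI (mean 27 to 30, SD 5 to 7) the loss is 37% to 40%. If the true effect were a step at 30, the split would lose nothing.

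In subjects, for the BMI coefficient only: 420 × 0.97 ≈ 407 analysed. At 25% the split is worth 407 × 0.539 ≈ 219 subjects, and at 40% 407 × 0.622 ≈ 253.

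In power: a BMI effect with 80% power when continuous has power Φ[(1.960 + 0.842)√R − 1.960] after the split. At 25% this is Φ(2.802 × 0.734 − 1.960) = Φ(0.097) ≈ 54%. At 40% it is Φ(2.802 × 0.789 − 1.960) = Φ(0.251) ≈ 60%.

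**Age.** Take the Section 6.4 bands and age uniform from 19 up to the 71st birthday. The bands are 17, 15 and 20 years wide, 52 in all. The share of variance lost within bands is (17³ + 15³ + 20³) / 52³ = 16,288 / 140,608 = 0.116, about 12%. For bell-shaped ages (mean 40 to 50, SD 10 to 12, cut to the eligible range) it is 17% to 22%.

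**AS03 contrast.** A simulation of a fit like Model 2B used 400 runs, 420 subjects in the ten planned cells, BMI with mean 28 and SD 6 as the only covariate, and a linear slope of −0.03 residual SD per unit. Power for the BMI term fell from 0.95 to 0.79. The standard error of the average AS03 contrast was 0.1009 with continuous BMI and 0.1015 with the split.

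**The case against.** The strongest reply is that age and BMI are not what these models are for. Section 8.3.2 says the models test prior vaccination and AS03, with age and BMI as adjustment covariates. The matching endpoint in Section 3.2.3 is response by age, sex and BMI, which reads as a grouped summary, and Tables 28-33 deliver it. Protocol Section 11.6.3 says only that covariates may be considered in modelling. Section 6.4 calls the analyses exploratory and says the study was not powered for subgroups. Using the same categories in tables and models is coherent, and three age bands can show a non-monotone pattern that one straight line cannot.

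Most of this stands. It means that no primary or secondary endpoint summary is touched and that nothing promised is missing. It does not supply a reason to discard the finer values in the only models that estimate these effects. The point about non-monotone age is met by a quadratic term.

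A reader might go further and infer that the adjusted comparison of primed with naïve subjects is materially confounded by age, because priming history is not randomized. The documents do not support that. They give no age distribution by stratum, and three bands already capture about 88% of the age variance if age is uniform. Any residual confounding is probably small and cannot be sized.

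**Conclusion.** The point holds as a modelling improvement, not as an error that threatens the trial's main results. Under a linear effect and roughly normal BMI, the split costs about 38% to 46% of the information on the BMI effect for shares of 25% to 40% at or above 30. The three age bands cost less, about 12% to 22% across the age shapes tried. The documents establish neither the linear effect, nor the shape of BMI, nor the share at or above 30.

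It would be wrong to infer a flat 40% loss as a property of the plan, or a loss of subjects from the trial as a whole. The loss is conditional and falls on the age and BMI coefficients; AS03 is randomized within stratum and its precision barely moves. The overlap at age 35 needs no assumption: Sections 6.4 and 8.3.2 disagree.

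**What to change.** In Models 1B and 2B, replace the age bands with age per 10 years and the BMI split with BMI per 5 kg/m², both continuous. Prespecify a quadratic term for each to check linearity, and state what will be reported if it shows curvature. Change the age and BMI rows in the shells of Tables 38, 39, 42 and 43 to match.

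Keep categories for the descriptive Tables 28-29 and 32-33, with non-overlapping bands throughout: 19-35, 36-50 and 51-70 for age, <30 and ≥30 for BMI. Correct the 35-50 label in Sections 8.3.1 and 8.3.2 and in the shells, including baseline Tables 17 and 19.

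The cost is a short text edit. No new data, visits or subjects are needed. The linear terms use two parameters where the categories use three, and the two quadratic checks add two. The small downside is the linearity assumption, which those checks address.
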